9.6.4 Permitted dose adjustments and interruption of treatment

Patients will start with oral methotrexate (MTX) capsules at a weekly dose of 15 mg for 4 weeks. In case of intolerance or toxicity to MTX or MTX placebo, the weekly dose of MTX or MTX placebo can be tapered to 10 mg at week 4, with a further possible reduction to 7,5 mg at week 8; in case of persistent intolerance/toxicity, MTX or MTX placebo will be stopped at week 12. For safety reasons, the dose reduction rate can be adapted at the discretion of the investigator.

9.6.5 Duration of treatment

Refer to Section 7, Study design to find detailed information about the Phase A and B treatment duration.

9.6.6 Packaging and labeling of the IMP

Methotrexate placebo will be supplied as capsules of 2.5 mg for oral administration packed in HDPE (high density polyethylene) bottle, 40 capsules per bottle.

CTU-1 of the University Hospital Ghent will label the bottles.

9.6.7 Traceability, storage, return and destruction of the IMP

The methotrexate placebo capsules will be stored until time of randomization at the pharmacy of the Ghent university hospital; capsules will be stored in a locked room with a temperature logger (at a temperature between 15°C and 25°C).

9.7 Management of pSpA

In this study, the patients may also take NSAIDs and/or sulphasalazine which are registered drugs for the management of pSpA. All patients should take oral folic acid supplementation according to standard clinical practice.

10 Concomitant medication and treatment

The use of DMARDs (conventional synthetic, targeted synthetic or biological), NSAIDs and glucocorticoids, allowed prior to entry in the trial and/or during the trial (up to 3 months after last study drug administration) is summarized in table 1.

Table 1: Prior and concomitant use of DMARDs, NSAIDs and glucocorticoids.

Drug	Prior Exposure	Concomitant use
Adequate dose of methotrexate	Not allowed	(Study medication)

Adequate dose of sulphasalazine	Not allowed	(Escape medication)
Other csDMARDs (e.g. hydroxychloroquine, ...)	Allowed	Not allowed
tsDMARDs (with therapeutic effect on SpA)	Not allowed	Not allowed
bDMARDs (with therapeutic effect on SpA)	Not allowed	Not allowed, except golimumab (study drug)
NSAIDs	Stable ≤1 week before baseline	Allowed (incl. dose adjustment & stop)
Intra-articular glucocorticoid injection	Prior corticoid infiltrations are allowed provided that the necessary wash out (≥ 6 weeks) before biopsy is respected	Max. 2 injections between week 12 and 20
Short course oral glucocorticoids	Not allowed <6 weeks before baseline	Not allowed
Prolonged oral glucocorticoids	Not allowed	Not allowed
Intravenous or intramuscular glucocorticoids	Not allowed	Not allowed
Topical corticosteroid treatment for psoriasis	Allowed	Allowed
Topical treatment for uveitis	Allowed	Allowed

Non-steroidal anti-inflammatory drugs (NSAIDs)

All patients are allowed to be treated with NSAIDs provided that the dose is stable and not exceeding the maximum recommended dose. NSAID treatment should be stable for 1 week before the first study drug administration.

During the trial, NSAID intake should not exceed the maximum recommended dose; the dose can be adapted or even stopped at the discretion of the treating rheumatologist. The need for concomitant intake of NSAIDs, including changes in the dosing schedule, will be recorded (by calculating the NSAID-index). This index will be considered as a surrogate (in)efficacy marker.

From week 20, all concomitant oral medication should be kept stable until the assessment of the primary endpoint at week 24.

Intra-articular glucocorticoid injections

- Treatment with intra-articular glucocorticoid injection(s) for peripheral SpA symptoms are allowed provided that the necessary wash out (≥ 6 weeks) before biopsy is respected. In.
- In case of persistent severe arthritis, a maximum of 2 intra-articular glucocorticoid injections will be allowed (between week 12 (after the clinical evaluations) but before the week 20 assessment). The number of glucocorticoid injections will be considered as a surrogate (in)efficacy marker. When patients have received intra-articular injections, they will – by default – be considered as non-responders at week 24.

Investigational drugs

Prior use of any investigational drug of chemical or biological nature within a period of 30 days or 5 half-lives of the drug (whichever is longer) before the baseline visit is not allowed; concomitant use of these drugs is not allowed during the trial.

Vaccines:

Patient may not have received, or are expected to receive, any live virus or bacterial vaccination within 3 months prior to the first administration of study agent, during the trial, or within 3 months after the last administration of study agent.

In line with international management recommendations investigators should ensure that the vaccination status of patients with inflammatory rheumatic diseases is up to date; this would include booster vaccinations for influenza and Covid-19. At present there is no convincing evidence that these vaccines would interfere or create safety hazards in combination with the treatment strategies applied in the Spartacus trial.

All patients will receive oral folic acid according to standard clinical practice when using MTX.

Rescue therapy

There are essentially 3 types of “rescue therapy”:

- At week 12, a “Patient Acceptable Signs & Symptoms Improvement”-question (“PASSI”) will be asked. If the patient has not experienced an acceptable improvement of signs and symptoms, oral sulphasalazine at a dose of 2 g per day will be added to the blinded study medication.
- Between week 12 (after efficacy evaluation) and week 24, there is a possibility to inject a persistently swollen joint with glucocorticoids. This procedure can only be performed twice in this 12-week time-window.
- At week 24, there is an option to treat patients, that did not reach clinical remission with the blinded study medication, with open-label golimumab at the standard dose of 50 mg SC every 4 weeks. This option is also available at week 36 for patients that have remained on blinded study medication.

The use of concomitant medication will be recorded from screening until the patient's last study visit. During the screening visit all current medication will be recorded on the concomitant medication log: Medication name, indication, dosage, frequency, start- and stop date. During each trial visit, the change in medication use will be registered in this log. Supplements are not considered as medication.

11 Procedures and Study Flow-Chart

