8.2.2 Exclusion criteria

- Medical history of inflammatory arthritis of a different etiology than peripheral spondyloarthritis (e.g. rheumatoid arthritis, systemic lupus erythematosus, gout, ...).
- Prior adequate treatment with methotrexate and/or sulphasalazine.
- Prior exposure to any biologic therapy with a potential therapeutic impact on SpA.
- Treatment with any investigational drug of chemical or biological nature within a minimum of 30 days or 5 half-lives of the drug (whichever is longer) prior to the Baseline Visit.
- Subject is taking or has taken prohibited medications as outlined in Table 1 without meeting the mandatory washout period(s) relative to the baseline visit.
- Infection(s) requiring treatment with intravenous (iv) anti-infective agents within 30 days prior to the Baseline visit or oral anti-infectives within 14 days prior to the baseline Visit.

- Have a known hypersensitivity to human immunoglobulin proteins or other components of golimumab.
- History of central nervous system (CNS) demyelinating disease or neurologic symptoms suggestive of CNS demyelinating disease.
- History of listeriosis, histoplasmosis, chronic or active Hepatitis B infection, Hepatitis C infection, human immunodeficiency virus (HIV) infection, immunodeficiency syndrome, chronic recurring infections or active TB.
- (History of) chronic heart failure (CHF), including medically controlled, asymptomatic CHF.
- History of malignancy (including lymphoma and leukemia) other than a successfully treated non-metastatic cutaneous squamous cell or basal cell carcinoma or localized carcinoma in situ of the cervix.
- Have received any live virus or bacterial vaccination within 3 months prior to the first administration of study agent; patients who are expected to receive such vaccinations during the trial, or within 3 months after the last administration of study agent.
- Positive serum pregnancy test at screening.
- Female subjects who are breast-feeding.
- Clinically significant abnormal screening laboratory results as evaluated by the Investigator.
- Positive anti-cyclic citrullinated peptide (anti-CCP) antibody at screening if the titers are crossing 3 times the upper limit of normal.
- Subject is considered by the investigator, for any reason, to be an unsuitable candidate for the study.
- Subject with current symptoms of fibromyalgia that would confound evaluation of the patient.

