11.4 Study specific Procedures and Interventions

11.4.1 ‘SPARTACUS Phase A’

Phase A – Visit 1A: CLINICAL SCREENING (week -6 to -4 days)

- Informed consent.
- Check fulfilment of in- and exclusion criteria.
- Demographic data, symptom duration, medical history, incl. past anti-rheumatic treatment, smoking/alcohol status, and family history.
- Current medication (dose and duration).

- Latent Tuberculosis (TB) screening: chest X-ray (if not performed within the last 3 months), TB test (Mantoux PPD-test or Quantiferon), TB questionnaire (see Addendum 4).
- Patient reported outcomes:
 - Patient global assessment of disease activity (0-10 numerical rating scale).
 - Patient global assessment of pain (0-10 numerical rating scale).
- Physical examination.
- Vital signs (blood pressure, heart frequency).
- Weight, length.
- Rheumatological examination (see Addendum 5):
 - 78-Tender and 76-swollen joint count.
 - Dactylitis assessment.
 - Enthesitis assessment (SPARCC (SPondyloArthritis Research Consortium of Canada) Enthesitis Index).
 - Physician global assessment of disease activity (0-10 numerical rating scale).
- Laboratory investigation:
 - Diagnosis: HLA B27 (if not known), anti-CCP antibodies (if not determined within the last 12 months).
 - Screening: peripheral blood count, serum creatinine, uric acid, liver function tests (ALT, gamma-GT, Alkaline Phosphatase, LDH), Creatine Kinase. (laboratory evaluations considered “standard-of-care” daily practice for SpA patients treated with csDMARDs and TNFi). (the results of tests performed within the last month are allowed).
 - Serum pregnancy test.
 - Screening for Hepatitis B, Hepatitis C, HIV and CMV IgG. (if not determined within the last 3 months).
 - Disease activity: inflammatory parameters: erythrocyte sedimentation rate (ESR), C-reactive protein (CRP).

Phase A – Visit 1B: SYNOVIAL BIOPSY SCREENING (week -6 to -4 days)

Performed in one of the synovial biopsy sampling units

- Ultrasound evaluation of clinically swollen joints identified at visit 1A.
- Ultrasound-guided synovial tissue sampling of a representative swollen joint (see Addendum 6 for list of joints that can be sampled). In case of multiple small joint involvement, a joint with a score of 2 or more on Grey Scale/Power Doppler ultrasound assessment will be chosen to sample.
- Laboratory investigation: Research samples (4 x 8ml blood-CPT (Cell Preparation Tube) and 10ml serum)
- Check fulfilment of in- and exclusion criteria.

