	scr	Biopt	W0	W4	W8	W12	W16	W20	W24	W28	W36	W48	W60	
Informed Consent	X													
Inclusion/Exclusion crit	X	X	X											
synovial biopsy & Ultrasound		X												
Anamnesis ^a	X													
Current Medication	X		X	X	X	X	X	X	X	X	X	X	X	X
Adverse Events			X	X	X	X	X	X	X	X	X	X	X	X
Latent TB screening ^b	X					X			X		X	X	X	
Patient disease activity & pain NRS	X		X	X	X	X	X	X	X	X	X	X	X	X
BASDAI			X	X	X	X	X	X	X	X	X	X	X	X
BASFI, ASAS-HI, Health economic evaluations			X			X			X		X	X	X	
HAQ-SpA			X						X			X		
Post biopsy questionnaire		X												
(Targeted) Physical examination ^f	X		X	X	X	X	X	X	X	X	X	X	X	X
Vital Signs	X					X			X		X	X	X	
Length (only at screening), weight	X					X			X		X	X	X	
Smoking/alcohol status	X					X			X		X	X	X	
76SJC/78TJC, dactylitis, enthesitis (SPARCC)	X		X	X	X	X	X	X	X	X	X	X	X	X
BASMI, chest expansion, Psoriasis assessment			X			X			X		X	X	X	X
Physician global NRS	X					X			X		X	X	X	
HLA B27 ^c , anti-CCP AB ^d , HBV ⁱ , HCV ⁱ , HIV ⁱ , CMV IgG ⁱ	X													
Safety Lab tests ^e	X ^e			X	X	X	X	X	X	X	X	X	X	X
ESR, CRP	X		X	X	X	X	X	X	X	X	X	X	X	X
Serum Pregnancy Testing	X													
Research samples ^g		X	X ^h			X			X					
PASSI						X					X	X		
Assessment of clinical remission status						X			X		X	X	X	
Study drug admin/dispensation			X	X	X	X	X	X	X	X	X	X	X	
Study drug accountability				X	X	X	X	X	X	X	X	X	X	

^a Demographic data, symptom duration, medical history, past anti-rheumatic treatment, family history

^b v1A: chest X-ray (if not performed within the last 3 months), TB test (Mantoux PPD-test or Quantiferon), TB questionnaire; other visits: only TB questionnaire

^c If not known

^d if not determined within the last 12 months

^e At v1A (for visit 1A: results of tests performed within the last month are allowed), week 24, week 36, week 48, week 60: peripheral blood count, serum creatinine, uric acid, liver function tests (ALT, GGT, AP, LDH), CK

At week 4, week 12, week 28: peripheral blood count, serum creatinine, ALT

At week 8, week 16, week 20: at the discretion of the treating rheumatologist

At the unscheduled visit: at the discretion of the treating rheumatologist

^f Full physical exam at screening, targeted physical exam at the other visits

^g 4 x 8ml blood-CPT (the synovial biopsy sampling units will also collect 10ml serum; at week 12: only 10ml serum; ZNA Jan Palfijn will only collect serum at BL)

^h Only if no samples taken at visit 1B

ⁱ if not determined within the last 3 months

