Depending on the joint to be examined and biopsied, the patient is positioned lying down or sitting. The highest comfort of the patient is pursued. The procedure is carried out under strict aseptic conditions (i.e., sterile) and the necessary precautions are taken for this (use of sterile drapes around the relevant joint, thorough disinfection, face mask, gloves, sterile covering of the ultrasound probe). A comprehensive ultrasound examination of the relevant joint is first conducted to identify the correct structures and locate the best site for tissue sampling.

Actual procedure:

The trajectory that the biopsy needle will follow from the external skin surface to the tissue to be biopsied will be anesthetized using an injection of lidocaine. This should take effect for 3 to 5 minutes before the actual tissue collection will occur. In the meantime, the researcher and the assisting personnel will prepare the biopsy material. The ultrasound probe is steriley packaged and placed on the joint where the biopsy will take place. The researcher can form a clear image on the screen of where the biopsy will take place. The tip of the needle will first be inserted subcutaneously and this can be visualized by the researcher. This needle is then advanced along the trajectory until it reaches the tissue that one wants to biopsy. When the researcher is certain of the correct location in the joint, several biopsies (10-12) of the tissue will be taken while the needle remains in place. After sufficient tissue samples have been taken, excess fluid will be aspirated.

Aftercare:

The injection site is to be disinfected again and covered with a plaster or bandage. The patient must remain in the department for observation for up to 30 minutes after the biopsy. No specific monitoring is required. The patient is advised to contact the responsible or treating physician in case of pain, swelling, or redness of the biopsied joint within 5-7 days after the procedure. If desired, pain relievers (paracetamol, anti-inflammatories) can be taken, but this is not mandatory. Local ice application may also be done if the patient finds it necessary.

Addendum 6b:

Joints accessible for synovial tissue sampling

(Provided there has not been a steroid injection the last 6 weeks)

- Wrist
- Elbow
- Metacarpophalangeal joints (MCP)
- Proximal Interphalangeal joints (PIP)
- Knee
- Ankle
- Metatarsophalangeal joints (MTP)

Addendum 7a – 7k: Patient-Reported Outcomes

- a) BASDAI
- b) BASFI

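### The six-week washout for short-course oral glucocorticoids is counted from baseline and the one for injections from the biopsy, so Visit 1B samples are guaranteed only 0 to 38 days without oral steroid

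*Protocol*

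**What the plan says.** All references are to the Protocol.

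- **Oral steroid.** Section 10, Table 1, short-course oral glucocorticoids, prior exposure: "Not allowed <6 weeks before baseline". Section 8.2.2 enforces the table by excluding patients who took prohibited medication "without meeting the mandatory washout period(s) relative to the baseline visit".
- **Injected steroid.** The intra-articular row of the same table uses a different reference point: "Prior corticoid infiltrations are allowed provided that the necessary wash out (≥ 6 weeks) before biopsy is respected". The text below the table repeats this. Addendum 6b attaches a similar condition to the list of joints that may be sampled: "Provided there has not been a steroid injection the last 6 weeks". It does not mention oral steroid.
- **Timing of sampling.** Section 11.4.1 sets the biopsy visit as "Phase A – Visit 1B: SYNOVIAL BIOPSY SCREENING (week -6 to -4 days". Clinical screening has the same window: "Phase A – Visit 1A: CLINICAL SCREENING (week -6 to -4 days". Research blood is drawn at the biopsy visit: "Laboratory investigation: Research samples (4 x 8ml blood-CPT (Cell Preparation Tube) and 10ml serum".
- **Baseline blood.** Footnote h of the Phase A flowchart restricts the Visit 2 research samples: "Only if no samples taken at visit 1B". The Visit 2 list in section 11.4.1 carries the same condition.
- **Purpose.** Goal 3 in section 5.2 seeks baseline biomarkers of response to a TNF inhibitor by single-cell and epigenetic profiling. Section 4.1 adds that their ability to predict drug-free remission will be assessed.

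**The concern.** The protocol twice chose six weeks as the relevant steroid-free interval but tied it to two different events. For a local injection the interval protects the tissue sample. For a short oral course, which is a systemic exposure, it protects only the baseline visit, and the tissue and its paired blood are taken before that visit.

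The eligibility check repeated at Visit 1B does not close the gap, because a patient sampled well inside six weeks of an oral course can still satisfy the criterion as written. Where blood was drawn at Visit 1B, footnote h also removes the later draw that would meet six weeks.

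At stake is the interpretation of the baseline biomarker work. If some tissue and blood samples carry the effect of a recent oral course and others do not, part of the variation between patients may reflect prior medication and not the disease subset that goal 3 sets out to identify.

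**Working it through.** The protocol states no figure on this point, so there is none to reproduce. The check is day arithmetic.

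**Inputs**
- Oral washout W = 6 weeks = 42 days before baseline (Table 1; section 8.2.2). The bar applies to less than six weeks, so a last dose on day -42 is permitted.
- Biopsy lead time b = days from Visit 1B to baseline, from 4 to 42 (section 11.4.1).
- Comparison interval: 42 days before the biopsy, as set for injections (Table 1; text below it).

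**Formula.** Guaranteed oral-steroid washout at biopsy = W - b = 42 - b.

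| Visit 1B on day | 42 - b (days) | Short of 42 by (days) |
|---|---|---|
| -42 | 0 | 42 |
| -35 | 7 | 35 |
| -28 | 14 | 28 |
| -23 (mid-window) | 19 | 23 |
| -14 | 28 | 14 |
| -7 | 35 | 7 |
| -4 | 38 | 4 |

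The window holds 42 - 4 + 1 = 39 possible days. None gives 42, because the shortfall always equals b and b is at least 4.

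**Blood.** Research blood drawn at Visit 1B has the same 0 to 38 days. Blood drawn at Visit 2 (day 0) has at least 42.

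**How far apart the two reference points are.** If 42 days were counted from the biopsy, the last oral dose would lie 42 + b days before baseline: 46 days for a biopsy on day -4 and 84 for one on day -42. This only shows that the two ways of counting are not interchangeable; it does not say which is right.

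**Limits**
- Prolonged oral, intravenous and intramuscular glucocorticoids are barred as prior exposure in Table 1, so only short oral courses are concerned.
- Oral steroid between biopsy and baseline is excluded, because the 42-day bar spans the whole Visit 1B window.
- The value 0 requires a last dose, clinical screening and biopsy all on day -42. If the bar on concomitant use applies from consent, the last dose must precede consent and the minimum is 0 to 1 day.

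**The case against.** The strongest reply is that there is no contradiction. Section 8.2.2 counts Table 1 washouts from baseline and the oral row follows that rule. An injection into a joint that may be biopsied is a local matter, so tying it to the biopsy is natural. Addendum 6b lists joints, and a systemic drug would not be expected there. The different reference points could be deliberate.

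That reading explains Addendum 6b. It does not explain Table 1: the injection row is not limited to the biopsied joint, and no passage gives a reason why a systemic exposure needs no interval before tissue and blood are taken.

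Other parts of the objection stand, and they rule out stronger readings that a reader might infer:

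- **That samples are typically taken with no washout.** Zero is the edge of the window.
- **That the protocol promises untreated tissue.** It speaks of biomarkers at baseline. It allows NSAIDs and prior use of other csDMARDs without setting a washout before the biopsy.
- **That exposure goes unrecorded.** Visit 1A takes past anti-rheumatic treatment and current medication, and section 10 asks for start and stop dates in the medication log. Applying the six-week rule itself requires knowing when the course ended.
- **That recent steroid users are sampled early, or are the more severe cases.** Nothing in the protocol shows either. Entry requires global and pain scores of at least 4 at screening, and the biopsy is taken from a swollen joint, which works against sampling a patient whose disease is currently suppressed.
- **That the trial's main result is affected.** No tissue or blood biomarker is among the endpoints in sections 6.1 and 6.2.

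How samples are selected for biomarker analysis may also be set out in an analysis plan or laboratory procedures that are not at hand. The reference point of the washout and the rule for redrawing blood, however, are fixed in the protocol itself.

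**Conclusion.** The point holds as a limited inconsistency in sampling rules. As written, the protocol guarantees 0 to 38 days between the last short-course oral glucocorticoid dose and the Visit 1B biopsy and blood. It never guarantees the 42 days set for injections, and where blood was taken at Visit 1B it omits the baseline draw that would have at least 42.

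This rests on six weeks being 42 days, on exactly six weeks being permitted, and on the Visit 1B window as stated. It concerns guaranteed minimum intervals: an individual patient's interval may be much longer. The number of patients with a recent oral course is not given, so the effect on the biomarker results cannot be sized. A reader might infer that steroid exposure will be mistaken for a predictor of response. The documents support only that the rules do not prevent this. The randomised comparison, the primary endpoint and the sample size are untouched.

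**What to change.** 1. Reconcile the oral and injection rows of Table 1, the washout criterion in section 8.2.2, Addendum 6b and the Visit 1B window, so that the protocol states whether the oral interval is also meant to protect the Visit 1B samples. Which reference point applies is for the sponsor to decide.
2. For every Visit 1B sample, including those already taken, derive the days from the last oral glucocorticoid dose to sampling from the medication records. Flag samples inside the protocol's own six-week interval.
3. Run the baseline biomarker analysis with and without flagged samples, or adjusted for the interval. Outright exclusion is not needed, since the tissue is scarce.
4. Amend footnote h and the matching line under Visit 2 so that flagged patients have research blood drawn at Visit 2, which is already scheduled.

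The cost is a short amendment, a few extra blood draws and a slightly smaller tissue set in the sensitivity analysis. Steps 2 to 4 leave study treatment and trial eligibility unchanged.
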